## 6.3. Handling of Dropouts or Missing Data

### 6.3.1. *Handling Missing Data from Patient Dropouts*

A likelihood-based mixed effects model for repeated measures will be used to handle missing data. The model parameters are simultaneously estimated using restricted likelihood estimation incorporating all of the observed data. Estimates have been shown to be unbiased when the missing data are missing at random and when there is ignorable non-random missing data.

Repeated measures and disease progression model analyses will only use data from visits where the data was scheduled to be collected (Andersen and Millen 2013). When patients discontinue from the study early, there may be efficacy or safety data measurements at visits where the variables were not scheduled to be collected. This data will be used in all other analyses.

### 6.3.2. *Handling Missing Items in Calculating Totals*

If any of the individual items for ADAS-Cog or ADCS-ADL are missing or unknown, every effort will be made to obtain the score for the missing item or items.

For ADAS-Cog13, if fewer than 4 of a total of 13 items are missing, the total score (maximum =85) will be imputed as follows: the total from the remaining items will be multiplied by a factor that includes the maximum score for the missing items. For example, if the first item, "Word-Recall Task," which ranges from a score of 0 through 10 (maximum = 10), is missing, and the second item "Commands," which ranges from a score of 0 to 5 (maximum = 5), is missing, then the multiplication factor =  $85/(85 - [10 + 5]) = 85/70 = 1.21$ . Thus, the total score for this example will be the sum of the remaining 11 items multiplied by 1.21. The

imputed number will be rounded up to the nearest integer. If more than 4 items are missing, the total score for ADAS-Cog13 at that visit will be considered missing.

For the ADCS-iADL, if <30% of the items are missing, the total score will be imputed (maximum = 59). The sum of the nonmissing items will be prorated to the sum of total items. The imputed number will be rounded up to the nearest integer. If the nearest integer is greater than the maximum possible score, the imputed score will be equal to the maximum score. If >30% of the items are missing, the total score for ADCS-iADL at that visit will be considered missing. The same imputation technique will be applied to the ADCS-ADL total score. Note that, depending on the specific item responses that are missing, it is possible to have an imputed total score for both the ADCS-iADL and the ADCS-ADL, an imputed total score for one but not the other, or both total scores missing.

The same imputation technique will be applied to the CDR-SB. If only 1 box (of 6) of the CDR is missing, the sum of the boxes will be imputed by prorating the sum from the other 5 boxes. If the score from more than 1 box is not available, the CDR-SB at that visit will be considered missing.

The iADRS score is calculated as follows:  $iADRS \text{ score} = [-1(ADAS - Cog_{13}) + 85] + ADCS-iADL$  (Wessels et al. 2015). If either ADAS-Cog13 or ADCS-iADL is missing, iADRS score will be considered missing.

For all other scales, if any item is missing, any total or sum involving that item will be considered missing.

### **6.3.3. Handling Missing Date Information**

For previous medications and medical history if parts of dates are missing, the following imputations will be performed:

- For start dates
  - a. if DAY is unknown, it will be set to 01
  - b. if MONTH is unknown, it will be set to JAN (01)
  - c. if Day and Month are unknown, it will be set to 01 and JAN (01)
  - d. if year is unknown, then start date is missing
- For end dates
  - a. if DAY is unknown, it will be set to 30
  - b. if MONTH is unknown, it will be set to DEC (12)
  - c. if Day and Month are unknown, it will be set to 30 and Dec (12)
  - d. if year is unknown, then end date is missing

## 6.4. Multicenter Studies

This study will be conducted by multiple investigators at multiple sites internationally. In the event that there is an inadequate number of subjects (defined as 1 or 0 randomized subjects per treatment group) at a site for the planned analyses, the following strategy will be implemented. Data from all such sites will be pooled. The pooling will be done first within a country. If the resulting pool within a country is still inadequate (1 or 0 randomized subjects to 1 or more treatment arms), no further pooling will be performed. The pooled site variable for each patient will be the country code if site was pooled; otherwise, it will be the site number. A listing including country, investigator site with address, number of patients enrolled (randomized) by each site, and unique patient IDs will be presented.

## 6.5. Multiple Comparisons/Multiplicity

A graphical strategy may be used for testing key secondary hypotheses to protect against Type I error of falsely rejecting a null hypothesis (Section [6.11.2.](#)). The use of a prespecified analysis plan that employs Bretz' graphical approach will provide strong control of the study-wise Type I error rate for the primary and key secondary hypotheses at level  $\alpha=0.05$  (Bretz et al. 2009, 2011).

## 6.6. Analysis Populations

For purposes of analysis, populations are defined in Table 6.6.1 and Table 6.6.2. These tables also list the study measures that will be summarized and/or analyzed for each population.

**Table 6.6.1. Analysis Populations for Study I8G-MC-LMDC**

Population	Description
Entered	All participants who sign informed consent
Randomized	All entered patients who are randomized to study treatment
Evaluable Efficacy	All randomized patients with at least one post-baseline iADRS13 result (protocol refers to this as the Full Analysis Set)
Safety	All randomized participants who take at least 1 dose of double-blind study treatment. Participants will be analyzed according to the actual treatment group received (actual treatment group is defined as the treatment received at Visit 2).
Per-Protocol	All subjects in the Evaluable Efficacy population who also: 
 
signed the inform consent form
 
had an assessment of the primary endpoint at each scheduled visit completed
 
had no violations of inclusion/exclusion criteria
 
had no study dosing algorithm violation (such as if subjects randomized to treatment A were given treatment B or subjects randomized to treatment A never received the assigned study drug)
 
had no unqualified raters and no raters with substantial scoring errors for the primary measure
 
were not considered non-compliant with regard to study drug (a subject is considered non-compliant when missing or incomplete infusions exceed 20%, OR if missed more than 3 consecutive infusions at any point)
 

Completers	All randomized subjects who have treatment disposition status of complete.
------------	--

**Table 6.6.2 Efficacy and Safety Measures Summarized and/or Analyzed for Each Analysis Population**

Population	Variables Assessed
Entered	Listings
Randomized	Tables and Listings for patient characteristics, baseline severity, and patient disposition
Evaluable Efficacy	Tables, Listings and/or Figures of the following: iADRS, ADAS-Cog 13 , ADCS-ADL (basic, instrumental and total), CDR-SB, MMSE, CBB, DCTClock, plasma total tau, plasma p-tau (181 and 217), plasma NfL, flortaucipir parameters, volumetric MRI measurements, and concomitant medications.
Safety	Tables, Listings and/or Figures of the following: Compliance, adverse events, laboratory results, vital signs, weight, ECG, safety MRIs, and C-SSRS.
Per-Protocol	Tables, Listings and/or Figures of iADRS, ADAS-Cog 13 , ADCS-ADL (basic, instrumental and total), CDR-SB, MMSE
Completers	Tables, Listings and/or Figures of iADRS, ADAS-Cog 13 , ADCS-ADL (basic, instrumental and total), CDR-SB, MMSE, plasma total tau, plasma p-tau (181 and 217), NfL, flortaucipir parameters, and volumetric MRI measurements

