## 6.10. Concomitant Therapy

Prior medications are defined as those that stop before randomization (the day prior to the first administration of study drug). Concomitant medications are defined as those being taken on or after randomization (the day prior to the first administration of study drug). A summary of concomitant medications will be presented as frequencies and percentages for each treatment group. Fisher's exact test will be used to test for treatment differences between groups. If the start or stop dates of therapies are missing or partial to the degree that determination cannot be made of whether the therapy is prior or concomitant, the therapy will be deemed concomitant. A summary table will also be provided for concomitant AChEI/memantine medications.

Medications will be coded using the World Health Organization (WHO) drug dictionary. Concomitant medications will be listed.

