### **6.16.1. Interim Analysis 1**

The objective of the first interim analysis (IA1) is to assess the viability of continuing with at least 1 dose of LY3303560 with regard to safety. An unblinded DMC review for safety will be conducted once approximately 30 patients have completed 3 months of exposure to study treatment (i.e., after completing 4 weeks following the third dose of study treatment). No patients beyond this initial group of approximately 30 patients will be dosed until the DMC review has been completed and the recommendation is to continue the study. This initial group will continue treatment during the assessment period. No statistical adjustments will be made to account for this interim since it is a safety only interim and there is no possibility of stopping for efficacy.

The following analyses will be included in IA1:

- Summary of Patient Disposition
- Summary of Patient Compliance
- Summary of Patient Demographics
- Summary of Patient Baseline Severity
- Summary of Patient Exposure
- Summary of Concomitant Medications
- Summary of Concomitant AChEI/Memantine Medications
- Summaries of Adverse Events (SAEs, DCAE's, TEAE's)

- Listing of Adverse Events
- Summaries of Laboratories (Categorical and Mean Change from Baseline)
- Listing of Laboratories
- Summaries of Vital Signs and Weight (Categorical and Mean Change from Baseline)
- Listing of Vitals Signs and Weight
- Summaries of ECGs (Categorical and Mean Change from Baseline)
- Listing of ECGs
- Summary of Safety MRIs
- Listing of MRIs
- Summary of C-SSRS
- Listing of C-SSRS

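### Table 6.6.2 puts concomitant medications on the Evaluable Efficacy population, so dosed patients with no post-baseline iADRS are in the adverse event tables but not in the medication table

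*SAP*

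**What the plan says.** Section 6.6 gives its two tables the job of linking measures to populations: "These tables also list the study measures that will be summarized and/or analyzed for each population".

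- **Evaluable Efficacy**, defined in Table 6.6.1: "All randomized patients with at least one post-baseline iADRS13 result". In Table 6.6.2 the list for this row ends with "flortaucipir parameters, volumetric MRI measurements, and concomitant medications".
- **Safety**, defined in Table 6.6.1: "All randomized participants who take at least 1 dose of double-blind study treatment". Its list in Table 6.6.2 is "Compliance, adverse events, laboratory results, vital signs, weight, ECG, safety MRIs, and C-SSRS". Concomitant medications are not on it.

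Section 6.10 describes the output ("A summary of concomitant medications will be presented as frequencies and percentages for each treatment group") and the comparison ("Fisher's exact test will be used to test for treatment differences between groups"). It adds a separate table for AChEI/memantine and a listing, and names no population for any of these. The interim output lists in section 6.16 include the item "Summary of Concomitant Medications", also without a population.

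**The concern.** Having a post-baseline iADRS is an event after randomization, and it has no bearing on whether a patient took another drug. Making it a condition for entering the medication table removes patients who were exposed to study drug but left early. Their adverse events stay in the safety tables, while any treatment given for those events leaves the medication table.

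Two things are at stake. First, the adverse event and medication tables would have different denominators, so they could not be read side by side. Second, the between-arm Fisher's exact test on medications would be made in a set selected after randomization. If more patients leave early in one arm than in another, the medications that they started are removed unequally.

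The restriction also sits oddly with section 6.10, which is inclusive elsewhere: a therapy whose dates cannot settle whether it was prior or concomitant is counted as concomitant.

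**Working it through.** The SAP states no figure on this point, so there is none to reproduce. The check is a comparison of the text, followed by an illustration of size.

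**1. Who is left out.** Evaluable Efficacy is randomized plus at least one post-baseline iADRS. Safety is randomized plus at least one dose. The patients in Safety but not in Evaluable Efficacy are those dosed with no post-baseline iADRS. They are in the adverse event, laboratory, vital sign, weight and ECG tables and absent from the medication table.

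**2. Does anything override Table 6.6.2?** Section 6.10 names no population. Section 6.1 sets intention-to-treat as the default unless otherwise specified, and Table 6.6.2 does specify. For the final report, Table 6.6.2 is the rule that applies.

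**3. Size under an assumed loss.** The SAP does not give the first post-baseline iADRS visit, so the loss has to be assumed. It gives two study sizes: about 225 patients on the title page and 360 in section 5.2. With 1:1:1 allocation these are 225/3 = 75 and 360/3 = 120 per arm.

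| Assumed share with no post-baseline iADRS | 75 per arm | 120 per arm |
|---|---|---|
| 3% | 75 × 0.03 = 2.3 | 120 × 0.03 = 3.6 |
| 8% | 75 × 0.08 = 6.0 | 120 × 0.08 = 9.6 |

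**4. Is 3 to 8% a reasonable range?** Section 5.2 assumes 30% dropout. Spread over 104 weeks at a constant hazard (an assumption), the share leaving before week w is 1 − (1 − 0.30)^(w/104). Assume also that no iADRS is taken at discontinuation.

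| First iADRS at (assumed) | Share lost | Of 225 | Of 360 |
|---|---|---|---|
| Week 4 | 1 − 0.70^(4/104) = 1.4% | 3.1 | 4.9 |
| Week 12 | 1 − 0.70^(12/104) = 4.0% | 9.1 | 14.5 |
| Week 24 | 1 − 0.70^(24/104) = 7.9% | 17.8 | 28.4 |

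These are totals over three arms. The range of 3 to 8% roughly matches a first iADRS between Weeks 12 and 24. An earlier first visit would give less.

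**The case against.** The strongest defence is that the choice may be deliberate. AChEI/memantine use at baseline is a covariate in the primary model, and the one additional table in section 6.10 is for those drugs, so a medication summary on the efficacy set helps to interpret efficacy. The SAP contains no wrong figure here. This stands as a reason to keep an AChEI/memantine table on that set. It is not a reason to restrict the summary of all concomitant medications, and the SAP gives none.

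A reader might also infer more than the document supports:

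- **That the data monitoring committee saw truncated medication tables.** Section 6.1 puts the interim safety analyses within the SAP's scope, but section 6.16 names no population for any interim table. The reviews also came before this version. The first had to be completed before anyone beyond the initial group of about 30 was dosed, and section 6.1.1 has enrolment complete by 1 March 2020. Counting 76 to 80 weeks from that date puts the third review's data point in August to September 2021, and this version is stamped 11 October 2021. What earlier versions said is not known. For the same reason, the arithmetic that one patient is 10% of an arm at the first review (30/3 = 10) is not evidence of harm.
- **That every early leaver is lost.** The definition does not require the iADRS to be at a scheduled visit. Section 6.3.1 expects that patients who discontinue early may have off-schedule efficacy data. An iADRS taken at discontinuation would keep such a patient in.
- **That the two tables use materially different arm definitions.** Safety tables group by treatment received and the default groups by allocation. Under sections 6.1 and 6.6 these differ only after a dosing error, and nothing in the SAP points to any.
- **That safety events go missing.** Adverse events, laboratory results, vital signs and ECGs are on the Safety population, and withdrawal is compared in all randomized patients. The medication listing may still show the excluded patients.

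**Conclusion.** The point holds for the final concomitant-medication table and its Fisher's exact test. As written, the SAP drops dosed patients with no post-baseline iADRS from that table while keeping them in the safety tables, and the comparison is open to selection if early leaving differs by arm.

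The number affected is unknown and probably small. The range of 2 to 6 patients per arm at 225, or 4 to 10 at 360, rests on the assumed 3 to 8% loss and on no iADRS being taken at early discontinuation. No success criterion, threshold or error rate depends on the medication table, so the primary inference is unaffected. This is a minor reporting weakness.

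**What to change.** In Table 6.6.2, move concomitant medications from the Evaluable Efficacy row to the Safety row, and name the Safety population in section 6.10. Every dosed patient is then in the medication table, and its denominator matches that of the adverse event tables. The only patients whom the move could remove are any who were randomized and never dosed but have a post-baseline iADRS; they are outside the adverse event tables as well.

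If medication use is wanted for interpreting efficacy, repeat only the AChEI/memantine table on the Evaluable Efficacy population and label it so.

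The cost is one line in Table 6.6.2, a phrase in section 6.10 and a changed population flag in the table program. Sample size, power and alpha do not change.

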## 6.7. Patient Disposition

Because this is a long-term study in a patient population that is elderly with multiple comorbidities, patient withdrawal is of particular concern. Additional efforts will be undertaken to reduce patient withdrawals and to obtain information on patients who are initially categorized as lost to follow-up.

From the randomized population, the percentage of patients withdrawing from each treatment group will be compared between groups using Fisher's exact test. Comparisons using Fisher's exact test will be done for the overall percentage of patients who withdraw and also for each specific reason for withdrawal.

The median time to discontinuation will also be compared between treatment groups using the Kaplan-Meier product limit estimator. For any-cause discontinuation as well as discontinuation due to adverse event or death, comparisons of time-to-discontinuation will be conducted using the Kaplan-Meier product limit estimator and the associated log-rank test.

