# 1. Statistical Analysis Plan: I8G-MC-LMDC: Assessment of Safety, Tolerability, and Efficacy of LY3303560 in Early Symptomatic Alzheimer's Disease

## Confidential Information

The information contained in this document is confidential and the information contained within it may not be reproduced or otherwise disseminated without the approval of Eli Lilly and Company or its subsidiaries.

**Note to Regulatory Authorities:** This document may contain protected personal data and/or commercially confidential information exempt from public disclosure. Eli Lilly and Company requests consultation regarding release/redaction prior to any public release. In the United States, this document is subject to Freedom of Information Act (FOIA) Exemption 4 and may not be reproduced or otherwise disseminated without the written approval of Eli Lilly and Company or its subsidiaries.

LY3303560

Alzheimer's disease

Multicenter, randomized double-blind, placebo-controlled, Phase 2 study comparing up to 5600 mg of LY3303560 with placebo over 104 weeks in approximately 225 patients with early symptomatic AD.

Eli Lilly and Company  
Indianapolis, Indiana USA 46285  
Protocol I8G-MC-LMDC  
Phase 2

SAP electronically signed and approved by Lilly on date provided below:

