### 5.2. Determination of Sample Size

Based on the Disease Progression Model (DPM), 360 enrolled patients, a 30% dropout rate, and a 3-month delay of treatment effect onset, this sample size will provide more than 95% power to

demonstrate that at least one of the active treatment arms has slowed cognitive/functional decline. This claim of slowing cognitive/functional decline is based on showing that at least one of the active treatment arms has a  $\geq 0.6$  posterior probability of slowing of iADRS progression over placebo by at least 4 points (that is, 25% slowing relative to placebo, based on a mean change from baseline in the placebo group of 16 points and mean change from baseline on at least one of the active treatment arms of at most 12 points) after 104 weeks (approximately 24 months) on study treatment. This power calculation comes from simulations using a placebo decline of 19.56 points and 33% slowing on 1400 mg LY3303560 and 50% slowing on 5600 mg LY3303560 relative to placebo at 104 weeks. The variance-covariance matrix in the simulations had a variance at Week 104 of 436.85 (equal to a standard deviation of 20.9). If both active treatment arms are placebo-like with no efficacy, the probability of passing the efficacy criterion specified above (that is, false positive) is approximately 2.5%. To test the hypothesis of a disease progression benefit, we calculate the posterior probability of superiority in cognitive/functional slowing, and if it is above a pre-specified threshold (which controls the experiment-wise type I error at approximately 2.5%), then a claim of cognitive slowing will be made. The simulation for the power calculation and sample size determination was carried out in FACTS Version 5.5.

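### The Kaplan-Meier curve for discontinuation due to adverse event or death (SAP 6.7) slightly overstates the share of patients who actually stopped for that reason

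*SAP*

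**What the plan says.** SAP section 6.7 (Patient Disposition) plans three things.

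- Crude percentages by arm, compared with Fisher's exact test, for the "overall percentage of patients who withdraw and also for each specific reason for withdrawal".
- A median: "The median time to discontinuation will also be compared between treatment groups using the Kaplan-Meier product limit estimator".
- Time-to-event comparisons for discontinuation from any cause and, separately, for "discontinuation due to adverse event or death, comparisons of time-to-discontinuation will be conducted using the Kaplan-Meier product limit estimator", together with a log-rank test.

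The section does not say how a patient who leaves for a different reason is handled in the last of these. No cumulative incidence or competing-risk method is named anywhere in the SAP. The sample size section (5.2) assumes "360 enrolled patients, a 30% dropout rate".

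**The concern.** A patient who withdraws for another reason can no longer discontinue study treatment because of an adverse event or death. Those exits are competing events. With a cause-specific event and a plain Kaplan-Meier estimator, the usual default is to censor such patients when they leave. The estimator then assumes that the patients who remain stand in for them, as if they would later have stopped for an adverse event or death at the same rate. So 1-KM describes a trial in which nobody leaves for any other reason, not the trial that was run.

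What is at stake is descriptive: the level and time course of one planned curve per arm. Section 6.7 itself singles out withdrawal as a worry in an older population with comorbidities, so other-cause exits are to be expected. The report would also show two different end-of-study figures for the same event, the curve's endpoint and the tabulated percentage, with nothing in the SAP to explain the difference.

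**Working it through.** The SAP gives no figure for this analysis, so there is none to reproduce.

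**Inputs**
- Total dropout D = 0.30 (SAP 5.2).
- Share s of dropout that is due to adverse event or death: not in the SAP. It is an assumption, varied from 0.10 to 0.90.
- Arm size for the simulation: 120 (360 patients, 1:1:1) and 75 (the opening page of the SAP gives about 225 patients). Both were used.

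**Formulas** (constant, proportional cause-specific hazards; other dropouts censored for Kaplan-Meier)
- Total cumulative hazard: H = -ln(1 - D) = -ln(0.70) = 0.357.
- Actual cumulative share: s × D.
- Kaplan-Meier figure: 1-KM = 1 - exp(-sH) = 1 - (1 - D)^s.

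Example, s = 1/3: actual share 0.30/3 = 10.0%; 1-KM = 1 - 0.70^(1/3) = 11.2%.

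| s | Actual share | 1-KM | Excess (points) | Relative excess |
|---|---|---|---|---|
| 0.10 | 3.0% | 3.5% | 0.50 | 17% |
| 0.20 | 6.0% | 6.9% | 0.89 | 15% |
| 1/3 | 10.0% | 11.2% | 1.21 | 12% |
| 0.50 | 15.0% | 16.3% | 1.33 | 9% |
| 2/3 | 20.0% | 21.2% | 1.16 | 6% |
| 0.80 | 24.0% | 24.8% | 0.82 | 3% |
| 0.90 | 27.0% | 27.5% | 0.46 | 2% |

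**Sensitivity to total dropout.** The largest excess is 0.56 points at D = 20% and 2.54 points at D = 40%, both at s = 0.50.

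**Sensitivity to timing.** If all adverse event or death exits come first, the excess is zero. If all other exits come first, 1-KM = sD / (1 - (1 - s)D). For s = 0.50 this is 0.15/0.85 = 17.6% against 15.0%. Over s = 0.10 to 0.90 the excess in this extreme case is about 0.8 to 2.6 points.

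**Simulation** (5,000 trials, s = 1/3). The mean of 1-KM against the mean crude share was 11.2% against 10.0% at 120 per arm, and 11.2% against 9.9% at 75 per arm. 1-KM was at or above the crude share in every run.

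**Log-rank test.** With equal adverse event or death hazards and other-cause dropout of 10% in one arm and 35% in the other, the cause-specific log-rank test rejected in 5.1% of 5,000 trials at a nominal 5%. The test keeps its size.

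**The case against.** The strongest reply is that the plan uses Kaplan-Meier to compare arms and nowhere says that 1-KM will be reported as the share who stopped. Kaplan-Meier and the log-rank test also match each other, since both concern the cause-specific hazard. The actual shares are reported anyway, by reason in 6.7 and for discontinuation due to adverse events in 6.13.2 and 6.13.3. And the excess is small: the binomial standard error of a 10% share is √(0.1 × 0.9/120) = 2.7 points at 120 per arm and √(0.1 × 0.9/75) = 3.5 points at 75.

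Most of this stands. It does not change what the curve estimates: a planned estimate whose level sits above the observed share, with no statement of how it should be read. Nor do the crude percentages supply a time course.

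A reader might go further and infer that unequal other-cause dropout would create a false gap between arms. Take 10% for adverse event or death in each arm, with other-cause dropout of 25% against 10%. The curves end at 11.6% and 10.6%. But the cumulative cause-specific hazards in that example really differ: (10/35) × -ln(0.65) = 0.123 against (10/20) × -ln(0.80) = 0.112. Kaplan-Meier shows that difference correctly. The reverse also occurs: with one fixed adverse event or death hazard (1-KM 11.2%), the actual share falls from 10.9% to 8.8% as other-cause dropout rises from 5% to 40%. Neither estimator is free of this; they answer different questions. The SAP also gives only one overall dropout rate, so it offers no basis for assuming such an imbalance.

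**Conclusion.** The point holds as a minor one. For discontinuation due to adverse event or death, 1-KM overstates the cumulative share that actually stopped for that reason, by about 0.5 to 1.3 percentage points at 30% dropout. This rests on three assumptions: other dropouts are censored (the default, not written in the SAP), hazards are constant, and the adverse event or death share of dropout lies between 10% and 90%. Timing alone could move the excess between zero and about 2.6 points.

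The any-cause curve, the log-rank test, the crude per-reason percentages and the primary analysis are not affected. A reader might infer that the trial's tolerability findings are biased. The documents do not support that: this analysis sits under patient disposition, and time to discontinuation is not among the safety and tolerability assessments listed in SAP section 4.2.

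**What to change.** In section 6.7:

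- For discontinuation due to adverse event or death, present the Aalen-Johansen cumulative incidence by arm, with discontinuation for any other reason as a competing event.
- Keep the log-rank test for this event, labelled as a test of the cause-specific hazard, and state that patients leaving for other reasons are censored in it.
- Keep Kaplan-Meier for any-cause discontinuation.

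The cost is a sentence or two of SAP text and a standard procedure; no new data are needed. There is one small downside. The curve and the log-rank p-value will then address different quantities and can disagree, which is why the labelling is needed.
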